9.4 Sample Size Considerations

The overall sample size for the trial is 169 patients.

Main study: The primary comparison will include all eligible and treated patients, of whom 129 will be accrued and randomized equally, for a total accrual of 43 patients per arm. After adjusting for an ineligibility rate of 10%, the total required sample size for randomization is 144 patients. Using an overall one-sided 0.10 level log rank test for each comparison, this study will have 89% power to detect a 44% reduction in the PFS hazard rate of 0.173 to 0.096 based on the estimated accrual and follow-up period. Assuming exponential survival, this corresponds to an 80% improvement in the median PFS of 4 months on nivolumab alone to 7.2 months on nivolumab plus cabozantinib or on nivolumab plus cabozantinib and

ipilimumab. The number of PFS events needed to achieve this power is 74 events under the alternative hypothesis for each of the two primary comparisons.

Targeted therapy sub-study: Up to 25 additional patients may be enrolled in Arm T. The best objective response rate and PFS will be described for this group of patients. Accrual to the study will stop when the total accrual goal for the randomized study is reached, even if 25 patients have not been enrolled to Arm T. If 25 patients enroll to Arm T before accrual to the randomized part of the study is reached, then Arm T only will be closed. With 25 patients enrolled, the maximum width of the 2-sided 90% exact binomial confidence interval for the best objective response rate will be 35%; with as few as 10 patients enrolled, it will be 56%.

9.5 Projected Accrual

As reflected by our prior E1512 study, it is estimated that patient accrual will be approximately 10 patients per month. It is estimated that the accrual goal will be reached within approximately 15 months with a follow up period of approximately 9-10 months, for a total study duration of 25 months.

9.6 Gender and Ethnicity

Based on previous data from E1512 the anticipated accrual in subgroups defined by gender and race is:

Racial Categories	Ethnic Categories				Total	
	Not Hispanic or Latino		Hispanic or Latino			
	Female	Male	Female	Male		
American Indian/ Alaska Native	4	1	0	0	5	
Asian	1	1	0	0	2	
Native Hawaiian or Other Pacific Islander	1	1	0	0	2	
Black or African American	6	7	0	0	13	
White	78	65	1	1	145	
More Than One Race	1	1	0	0	2	
Total	91	76	1	1	169	

The accrual targets in individual cells are not large enough for definitive subgroup analyses. Therefore, overall accrual to the study will not be extended to meet individual subgroup accrual targets.

9.7 Randomization Scheme

Main study: Randomization to treatment will be determined using permuted blocks within strata with dynamic balancing on main ECOG-ACRIN institutions plus affiliates. The randomization will be stratified by known PD-L1 status (negative vs. positive ($\geq 1\%$) vs. unknown/not tested). It will be a 1:1:1 between arms A, B, and C.

9.8 Monitoring Plan

9.8.1 Interim Analysis: Efficacy

Main study: This study will also be monitored for futility and one interim analysis at roughly 50% information is planned for each comparison. At that time, if the point estimate of the PFS hazard ratio is consistent with detriment (HR > 1.0) on either of the two combination arms, then the data monitoring committee may consider terminating an arm early for overall lack of treatment difference.

9.8.2 Interim Analysis: Safety Monitoring

Interim analyses of toxicity are performed twice yearly for all ECOG-ACRIN studies. Reports of these analyses are sent to the ECOG-ACRIN Principal Investigator or Senior Investigator at the participating institutions. Expedited reporting of certain adverse events is required, as described in Section [5.2](#).

Because this is the first time that ipilimumab is being combined with nivolumab and cabozantinib in this population, close monitoring of toxicity is an important endpoint of the trial. We will collect data and conduct an interim safety analysis among the first 15 patients who have completed the first two cycles of treatment on each arm. This will be done without a planned suspension to accrual. The safety analysis will be done based on the case report form database and the CTEP-AERS database, although the focus will largely be placed on the CTEP-AERS data. The safety data will be reviewed with the sponsor (CTEP) to rule out the incidence of excessive toxicities. This preliminary toxicity analysis will occur in addition to the twice yearly monitoring for toxicity for the purposes of interim reporting.

In particular, there is concern for excessive rates of pneumonitis or colitis on the 3-drug regimen. With respect to colitis, prior studies have demonstrated that grade 3-5 colitis occurs in approximately 11% of patients with nivolumab and ipilimumab therapy. As such, if we observe 5 or more patients with grade 3-5 treatment-related colitis among 15 patients analyzed per arm, the lower bound of the two-sided 90% exact binomial confidence interval will have exceeded 11% and consideration may be given to terminating the arm associated with the higher rate of colitis.

With respect to pneumonitis, a similar approach will be used. Prior studies have demonstrated that grade 3-5 pneumonitis occurs in approximately 3% of patients treated with nivolumab and ipilimumab. Therefore, if we observe 3 or more grade 3-5 incidents of treatment-related pneumonitis in a cohort of 15 patients, then the lower bound of the two-sided 90% exact binomial confidence interval will have exceeded 3% and consideration may be given to terminating the arm associated with the higher rate of pneumonitis.

10. Specimen Submissions

Tumor tissue specimens must be submitted for defined laboratory research studies described in Section [11](#).

It is required that all specimens submitted on this trial be entered and tracked using the ECOG-ACRIN Sample Tracking System (see Section [10.2](#)). An STS shipping manifest form is to be included with every submission.

All specimens must be labeled clearly with the ECOG-ACRIN protocol number (EA5152), ECOG-ACRIN patient sequence number, patient's initials, collection date, and specimen type.

10.1 [Submissions to the ECOG-ACRIN Central Biorepository and Pathology Facility \(CBPF\)](#)

If you have any questions concerning tumor tissue submission please contact the ECOG-ACRIN CBPF at [contact] or [contact]

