5.2.10 Additional instructions, requirements and exceptions for protocol
EA5152

Additional Instructions

For instructions on how to specifically report events that result in persistent or significant disability/incapacity, congenital anomaly, or birth defect events via CTEP-AERS, please contact the AEMD Help Desk at [contact] or [contact]. This will need to be discussed on a case-by-case basis.

Reporting a death on study: A death occurring while on study or within 30 days of the last dose of treatment requires both routine and expedited reporting, regardless of causality. Attribution to treatment or other cause must be provided.

NOTE: A death due to progressive disease should be reported as a Grade 5 "Disease progression" under the System Organ Class (SOC) "General disorder and administration site conditions". Evidence that the death was a manifestation of underlying disease (e.g. radiological changes suggesting tumor growth or progression; clinical deterioration associated with a disease process) should be submitted.

EA5152 specific expedited reporting requirements:

- **Colitis:** Any grade 3-5 colitis that is considered treatment related must be reported in CTEP-AERS accessed via Medidata Rave within 24 hours of learning of the event, followed by a complete expedited report within 5 calendar days of the initial 24-hour report.
- **Pneumonitis:** Any grade 3-5 pneumonitis that is considered treatment related must be reported in CTEP-AERS accessed via Medidata Rave within 24 hours of learning of the event, followed by a complete expedited report within 5 calendar days of the initial 24-hour report.
- **Infusion Reactions:** Any grade 3-5 infusion reaction must be reported in CTEP-AERS accessed via Medidata Rave within 24 hours of learning of the event, followed by a complete expedited report within 5 calendar days of the initial 24-hour report.

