5.4.3 General principles for management of toxicity with combination therapy

The combinations of cabozantinib and immunotherapy are still investigational, and unanticipated or synergistic side effects may be observed. Toxicity from combination therapy may be difficult to attribute to cabozantinib versus nivolumab (with or without ipilimumab). Guidance is provided below in defining attribution by holding cabozantinib, or by empirically starting corticosteroids.

As a general approach, it is suggested that AEs be treated with supportive care when possible at the earliest signs of toxicity. The below management guidelines are provided based on what is known individually about cabozantinib and nivolumab/ipilimumab, with additional guidance in the areas of overlap. They are not mandatory and investigator discretion may be used.

There are many circumstances in which the instructions below dictate permanent discontinuation of therapy. If an investigator feels that it is in the patient's best interest to continue on study therapy, study chair approval may be obtained prior to restarting drug.

Table of relative likelihood of cabozantinib-related and immune-related toxicities.

++ More common

+ Less common

- Infrequent

Toxicity	Cabozantinib-related	Immune-related	Protocol management section
Diarrhea	++	++	5.4.6
Nausea and Vomiting	++	+	5.4.7
Oral mucositis	++	-	5.4.8
Hand-foot syndrome (palmar-plantar erythrodysesthesia syndrome)	++	-	5.4.8
Skin Rash	+	+	5.4.8
Transaminitis (AST/ALT increased)	+	++	5.4.9
Hyperbilirubinemia (bilirubin increased)	-	+	5.4.9
Amylase/lipase increased; pancreatitis	+	-	5.4.9
Pneumonitis	+	++	5.4.10
Hypothyroidism	++	++	5.4.11
Adrenal insufficiency	-	+	5.4.11
Neurologic events	-	+	5.4.12
Renal dysfunction	-	-	5.4.13
Proteinuria	+	-	5.4.13
Fatigue	++	++	5.4.14
Fever	-	-	5.4.15
Infusion reaction	N/A	-	5.4.16
Thrombosis/embolism	+	-	5.4.17
Hypertension	++	-	5.4.18
Cardiomyopathy/myocarditis	-	+	5.4.19
Hemorrhagic events	+	-	5.4.20
Fistula formation/perforation	+	-	5.4.21
Wound healing problems	+	-	5.4.22
Osteonecrosis of the jaw	+	-	5.4.23
Cardiac QTc prolongation	+	-	5.4.24

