5.4.5 Immune-related adverse events

Immune-related adverse events can happen with any onset in relationship to immune therapy administration, even months after discontinuation of therapy. Corticosteroids are the mainstay of therapy for immune-related adverse events. Most should improve or resolve with an adequate dose of steroids. Prior to starting corticosteroids or hormone replacement for any reason, appropriate endocrine testing including cortisol, ACTH, TSH and reflex T4 to document baseline is strongly recommended.

Please note that in some cases the treatment algorithms recommend steroids if symptoms do not resolve in 7 days. However, this recommendation is not meant to delay steroid treatment at any time it is clinically indicated. Any patient started on corticosteroids initially who is determined to not require steroid treatment for an autoimmune adverse event may resume therapy after an observation period without further symptoms at the discretion of the investigator. Any patients who require additional immune suppressive treatment beyond steroids should go off immune therapy study treatment (but may continue cabozantinib as appropriate).

If AE's are felt to be immune related and drugs are held, nivolumab and ipilimumab should either be given together or both held. Cabozantinib may be either continued, or held, as felt appropriate by the investigator depending on the particular toxicity. The study chair may be contacted for individual circumstances to provide additional guidance.

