5.4.10 Pneumonitis

[figure not shown]
Management of cabozantinib associated pneumonitis

Pneumonitis has been associated with cabozantinib, nivolumab, and ipilimumab therapies individually. In general it is difficult to definitively diagnose and can be life threatening. Patients with proven symptomatic clinically proven pneumonitis refractory to management guidelines for nivolumab +/- ipilimumab (below) should have cabozantinib permanently discontinued, if they were on cabozantinib therapy.

Pneumonitis	Management/Next Dose for Nivolumab+/-Ipilimumab
≤ Grade 1	Hold dose pending evaluation and resolution to baseline including baseline pO2. Resume no change in dose after pulmonary and/or ID consultation excludes lymphocytic pneumonitis.
Grade 2	Hold dose pending evaluation. Resume no change in dose after pulmonary and/or ID consultation excludes ipilimumab and associated lymphocytic pneumonitis as the cause of the pneumonitis. Off study if steroids are required. ^
Grade 3	Hold dose pending evaluation. Resume no change in dose after pulmonary and/or ID consultation excludes ipilimumab and associated lymphocytic pneumonitis as the cause of the pneumonitis. Off study if steroids are required
Grade 4	Off protocol therapy
Distinguishing inflammatory pneumonitis is often a diagnosis of exclusion for patients who do not respond to antibiotics and have no causal organism identified including influenza. Most patients with respiratory failure or hypoxia will be treated with steroids. Bronchoscopy may be required and analysis of lavage fluid for lymphocytic predominance may be helpful. Patients with new lung nodules should be evaluated for sarcoid like granuloma. Please consider recommending seasonal influenza killed vaccine for all patients.	
Recommended management: See Pulmonary Adverse Event Management Algorithm	

Pulmonary Adverse Event Management Algorithm

Rule out non-inflammatory causes. If non-inflammatory cause, treat accordingly and continue I-O therapy. Evaluate with imaging and pulmonary consultation.

Patients on IV steroids may be switched to an equivalent dose of oral corticosteroids (e.g. prednisone) at start of tapering or earlier, once sustained clinical improvement is observed. Lower bioavailability of oral corticosteroids should be taken into account when switching to the equivalent dose of oral corticosteroids.

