9.3 Statistical Analysis Plan

The primary and some secondary analyses will include all eligible and treated patients. Exceptions to this include: analysis of toxicity data, which will include all patients who received study drug regardless of eligibility, and analyses of response, which will include eligible and treated patients with measurable and evaluable disease.

Time-to-event data, such as PFS and OS, will be estimated using the Kaplan-Meier method, and Cox proportional hazards models will be used to estimate the treatment hazard ratios. The primary comparison of PFS will use a logrank test stratified on the randomization stratification factors with a one-sided type I error rate of 10%. Other comparisons of groups will be made using the logrank test and Cox modeling.

Categorical data, such as response rates (CR+PR) and toxicity, will be compared using Fisher's exact tests with a one-sided type I error rate of 10%; multivariable logistic regression modeling will be used to adjust for the effect of any covariates that are associated with these categorical outcomes. Though none are currently planned, any continuous outcomes will be analyzed using Wilcoxon rank sum test, and multivariable linear regression models may be used to adjust for multiple associations with outcome.

Modeling procedures will implement backward selection; variables significant at the 0.10 level in the univariate setting will be chosen for inclusion in an initial full model, and at each step the least significant variable will be removed from the model. Only those covariates with $p < 0.05$ will remain in any final models, unless there are factors identified by the study team as crucial to model interpretation.

Point estimates of all endpoints will be accompanied by the corresponding two-sided 80% confidence intervals.

In the event that there are missing data, no imputation of the missing data will be conducted. We will assume that data are missing at random and will conduct all analyses as originally planned because we do not anticipate an excess of missing data.

Subset analyses are planned for all stratification factors and all known prognostic factors, such as performance status, age, sites of metastases, gender, etc. Subset analyses of all variables, including correlatives, are considered to be exploratory in nature.

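### The 15-patient safety triggers are tied to two-cycle completers, so a patient who dies or stops for severe pneumonitis before day 56 may not be counted

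*Combined protocol and SAP*

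**What the plan says.** Section 9.8.2 (Interim Analysis: Safety Monitoring) plans an "interim safety analysis among the first 15 patients who have completed the first two cycles of treatment on each arm", without pausing accrual. A cycle is 28 days (Section 5.1), so two cycles end at day 56.

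Two numeric triggers follow in the same section. For pneumonitis, "if we observe 3 or more grade 3-5 incidents of treatment-related pneumonitis in a cohort of 15 patients", the lower limit of the two-sided 90% exact interval is above the 3% reference, and closing an arm may be considered. For colitis the trigger is 5 of 15, against an 11% reference. The data are the case report forms and the expedited-report database, and "the focus will largely be placed on the CTEP-AERS data".

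Three other places bear on who is counted:

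- Section 9.3 makes an exception to the eligible-and-treated population for the "analysis of toxicity data, which will include all patients who received study drug regardless of eligibility".
- Section 5.4.10 takes grade 4 pneumonitis off protocol therapy. For grade 3 it says "Off study if steroids are required", and it expects most patients with hypoxia or respiratory failure to receive steroids.
- Section 5.4.5 lets some patients stop immunotherapy and stay on cabozantinib. The protocol does not say whether such a patient has completed two cycles.

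**The concern.** The first 15 completers per arm are the only 15 patients that Section 9.8.2 identifies. Nothing says that patients who die or stop earlier are added back. Taken as written, inclusion in the count depends on surviving and tolerating treatment to day 56, and the monitored events can prevent exactly that. A fatal pneumonitis in cycle 1 is a grade 5 event, yet that patient can never be a two-cycle completer.

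These are the only numeric safety triggers in the plan. Section 9.8.2 also notes that ipilimumab has not been added to the doublet before in this population. If severe events leave the count, the trigger can stay silent when it should fire. The literal rule also departs, without explanation, from the all-treated toxicity population in Section 9.3.

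**Working it through.** **Inputs from the documents.** 15 patients per arm; trigger counts 3 (pneumonitis) and 5 (colitis); reference rates 3% and 11%; two-sided 90% exact binomial interval (all Section 9.8.2).

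**Assumed inputs, not in the documents.** p is the true rate of grade 3-5 treatment-related pneumonitis among treated patients. d is the share of affected patients who leave before completing cycle 2, and e is the same share among unaffected patients.

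**Step 1: reproduce the plan's thresholds.** The exact lower limit for x events in 15 is the 5% quantile of a Beta(x, 16 − x) distribution.

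| Events/15 | Lower limit | Comparison |
|---|---|---|
| 2 | 2.4% | below 3% |
| 3 | 5.7% | above 3% |
| 4 | 9.7% | below 11% |
| 5 | 14.2% | above 11% |

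The plan's figures hold. Each threshold is the smallest count that clears its reference. If one event is uncounted and replaced by an event-free completer, a met trigger becomes unmet.

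**Step 2: event rate among completers.**

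q = p(1 − d) / [p(1 − d) + (1 − p)(1 − e)]

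The rate is biased down if d > e, unbiased if d = e, and biased up if d < e. For example, p = 0.15, d = 0.50, e = 0 gives q = 0.075 / (0.075 + 0.85) = 0.081.

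**Step 3: chance of reaching the pneumonitis trigger,** P(Bin(15, q) ≥ 3), at p = 15%. Counting all treated patients, q = p and the chance is 39.6% whatever d and e are. Under the completer rule:

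| | d = 25% | d = 50% |
|---|---|---|
| e = 0 | q = 0.117, 25.2% | q = 0.081, 11.6% |
| e = 10% | q = 0.128, 30.1% | q = 0.089, 14.4% |
| e = 20% | q = 0.142, 36.1% | q = 0.099, 18.2% |

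In the reverse direction, d = 10% and e = 20% give q = 0.166 and 46.3%.

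**Step 4: sensitivity to the assumed true rate,** at d = 50%.

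| p | All treated | Completers, e = 0 | Completers, e = 20% |
|---|---|---|---|
| 10% | 18.4% | 4.1% | 6.9% |
| 15% | 39.6% | 11.6% | 18.2% |
| 20% | 60.2% | 22.8% | 33.1% |
| 30% | 87.3% | 50.9% | 64.3% |

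At p equal to the 3% reference, the all-treated count reaches 3/15 only 0.9% of the time, so counting everyone does not produce frequent false alarms.

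**Step 5: a rough guide to e.** Section 9.4 plans on PFS hazards of 0.173 and 0.096, consistent with its medians of 4 and 7.2 months. Day 56 is 56/30.44 = 1.84 months. The implied share with a PFS event by then is 1 − exp(−0.173 × 1.84) = 27% or 1 − exp(−0.096 × 1.84) = 16%. The first scan is due only in the week before cycle 3 (Section 7.1, footnote 11), so many progressions would surface around the end of cycle 2. These shares are upper-end guides to e, but e = 0 is the least plausible row.

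No trigger probability is given for colitis, because the text supports no value of d for it.

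**The case against.** **The completer clause may only time the look.** The trigger sentences refer just to 15 patients analyzed or a cohort of 15, and Section 9.3 could be read as the general rule that fills the gap. This reading is possible and the text does not exclude it. However, Section 9.3 does not mention the interim look, and Section 9.8.2 names no other 15 patients.

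**Early exit is not certain.** Of the toxicity guidance, Section 5.4.3 says "They are not mandatory and investigator discretion may be used", and it lets the study chair approve continuation. Section 5.4.10 requires permanent cabozantinib discontinuation only for pneumonitis refractory to the immunotherapy guidance. Section 5.4.5 notes that immune events can also come late, and an event after cycle 2 removes nobody from the set. All of this stands, and it is why d is left open. It does not help with deaths before day 56.

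**The size rests on assumptions.** The 15% rate is five times the reference, and p, d and e have no source in the documents. This stands too. The direction depends on d exceeding e, and the size varies widely.

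**Oversight does not rest on the count.** Section 5.2.10 states: "Any grade 3-5 pneumonitis that is considered treatment related must be reported in CTEP-AERS", within 24 hours. The same applies to colitis, and deaths on study or within 30 days of the last dose are also expedited. The look uses that database, twice-yearly toxicity reviews continue, and the triggers only prompt consideration. This limits the harm, but no section says that events in non-completers enter the 3/15 or 5/15 count.

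**Counting every early stopper dilutes the rate** with patients who leave quickly for progression. An alternative is to count completers plus toxicity stoppers only. At p = 15% and e = 20% that gives q = 0.15 / (0.15 + 0.68) = 0.181 and a trigger chance of about 53%. But it keeps every affected patient while dropping unaffected ones, so it overstates the rate. The all-treated count is unbiased and is the plan's own convention.

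**Conclusion.** The concern holds. Section 9.8.2, followed as written, leaves out a patient who dies of or stops for grade 3-5 pneumonitis before day 56. If the clause was meant only to set the timing, the wording does not say so. The loss of one event is enough to undo either trigger, and this needs no assumed rate. The probability effect does rest on assumptions. At a true pneumonitis rate of 15% and d = 50%, the chance of triggering falls from 39.6% to between 11.6% and 18.2% for e from 0 to 20%. It is unchanged at d = e and rises if d < e. What is weakened is the numeric signal, not safety oversight as a whole. This should be fixed, and it does not invalidate the design.

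**What to change.** In Section 9.8.2, define the cohort as the first 15 patients per arm who receive any study drug. Assess each at day 56, or at permanent discontinuation or death if earlier. State that early stoppers stay in the denominator and that their events count. If the two-cycle clause was meant only to time the look, say that explicitly. This brings the section into line with the toxicity population in Section 9.3 and removes the need to define completion for a patient who continues on cabozantinib alone.

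The cost is one or two sentences. The 3/15 and 5/15 thresholds and their confidence-limit rationale are unchanged, no patients are added, and the events concerned are already reported within 24 hours to the database that the look uses.

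Patients who leave early for progression will be in the denominator, as they already are in the Section 9.3 population. Reporting how many of the 15 left before day 56, and why, would let readers judge that dilution.

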5.1 Administration Schedule

Treatment should start within seven working days after registration.

Cycle = 4 weeks (28 days)

Cabozantinib will be dispensed every cycle.

Rev. Add1

NOTE: Cabozantinib should be taken on an empty stomach (i.e. do not eat 2 hours before or 1 hour after each dose of cabozantinib. Do not crush or chew. Do not take missed dose within 12 hours of the next dose. Please refer to [Appendix VII](#) for more information.

Patients will continue receiving treatment until disease progression is observed or an adverse event requiring discontinuation occurs.

All therapy should start on the same day, but cabozantinib may start the morning following infusional therapy if morning dosing is desired.

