5.1.3 ARM C

Nivolumab 480 mg IV over 60 minutes every 4 weeks, ongoing

Cabozantinib 40 mg PO daily, ongoing

Ipilimumab 1 mg/kg over 90 minutes every 8 weeks, ongoing

NOTE: On days when both nivolumab and ipilimumab are administered, nivolumab is administered prior to ipilimumab.

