 11. All efforts must be made to assess tumor from the same type of scan that was performed at baseline. A CT scan with contrast involving known systemic areas of disease is recommended. Imagine studies should be done within 4 weeks prior to registration and every 8 weeks (based on Cycle 1 Day 1) during treatment until PD. The imaging should be done within 7 days prior to cycle 3, 5, 7, 9 etc. but may be performed after the treatment for unusual circumstances such as holidays. If drugs are held, the imaging should still be performed every 8 weeks counting from Cycle 1 Day 1.
 12. Patients must have a brain MRI or head CT with contrast at baseline within 12 weeks prior to registration. Patients with known brain metastases at baseline must have a brain MRI or head CT within 4 weeks prior to registration. Patients with known brain metastases should have repeat imaging at least every 16 weeks (4 cycles). Repeat brain imaging is not required for patients without known brain metastases at baseline.
 13. Tumor tissue specimens are required to be submitted for defined laboratory research studies as outlined in Section 10.
 14. All specimens submitted must be entered and tracked via the online ECOG-ACRIN Sample Tracking System (STS).

15. Ipilimumab administration every 8 weeks (cycle 1, 3, 5, 7, etc.)
16. For Arm T patients, to be assigned a status of complete or partial response, changes in tumor measurements must be confirmed by repeat assessments performed no less than four weeks after the criteria for response are first met. Arm A, B, and C patients do not require confirmation scans for complete or partial response.
17. Tobacco use assessment PROs will be collected using EASEE-PRO.
18. Oral daily dosing

Rev. Add4

8. Drug Formulation and Procurement

This information has been prepared by the ECOG-ACRIN Pharmacy and Nursing Committees.

Availability

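### The only numeric colitis and pneumonitis check is applied once, at a milestone that guarantees just one ipilimumab dose, with no event cutoff or benchmark exposure period stated

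*Combined protocol and SAP*

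**What the plan says.** Section 9.8.2 justifies close toxicity monitoring by the first use of ipilimumab with nivolumab and cabozantinib in this population. It plans one "interim safety analysis among the first 15 patients who have completed the first two cycles of treatment on each arm", without pausing accrual.

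For colitis, the section takes as its benchmark that "grade 3-5 colitis occurs in approximately 11% of patients with nivolumab and ipilimumab therapy". The trigger is met "if we observe 5 or more patients with grade 3-5 treatment-related colitis among 15 patients analyzed per arm". For pneumonitis, the benchmark is that "grade 3-5 pneumonitis occurs in approximately 3% of patients treated with nivolumab and ipilimumab", and the trigger is 3 of 15. Each count is chosen so that the lower limit of a two-sided 90% exact interval lies above the benchmark. Reaching it allows termination of the affected arm to be considered; it does not require it.

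The exposure behind the milestone follows from three other places:

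- Section 5.1: "Cycle = 4 weeks (28 days".
- Section 5.1.3, Arm C: "Ipilimumab 1 mg/kg over 90 minutes every 8 weeks, ongoing".
- Section 7.1, footnote 15: "Ipilimumab administration every 8 weeks (cycle 1, 3, 5, 7, etc".

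On timing of onset, section 5.4.5 says: "Immune-related adverse events can happen with any onset in relationship to immune therapy administration, even months after discontinuation of therapy".

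**The concern.** The check exists mainly because of the three-drug arm, and its milestone falls one day before the first repeat ipilimumab dose is due. Section 9.8.2 does not say whether events after the second cycle count, when the data are cut, or what length of treatment and follow-up produced the 11% and 3%. Two analysts could therefore apply the same rule to different amounts of exposure and both be following the protocol. Neither could show that the observed rate and the benchmark cover comparable periods.

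At stake is the sensitivity of the only quantitative criterion for these two toxicities. If part of the excess appears after the events counted at this one look, the count can stay below the trigger and be read as reassurance while enrolment continues. No later numeric criterion would correct that reading.

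**Working it through.** **1. The plan's own thresholds.** The exact lower limit is the 5% quantile of a Beta(x, 16 − x) distribution.

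- Colitis: 4/15 gives 9.7% and 5/15 gives 14.2%, so 5 is the smallest count above 11%.
- Pneumonitis: 2/15 gives 2.4% and 3/15 gives 5.7%, so 3 is the smallest count above 3%.
- Chance of reaching the trigger at the benchmark: P(X ≥ 5 | 15, 0.11) = 1.9%; P(X ≥ 3 | 15, 0.03) = 0.9%.

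The threshold arithmetic is correct.

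**2. Ipilimumab doses guaranteed.** Two cycles are 2 × 28 = 56 days. Doses are due on days 1, 57, 113 and so on, so completing two cycles guarantees one dose. The ±3-day visit window (section 7.1, footnote 2) would allow the second from day 54, but does not guarantee it.

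**3. Exposure if all follow-up counts.** Inputs are 10 patients per month (section 9.5), 144 of 169 randomised (section 9.4) and 1:1:1 allocation (section 9.7). Arm C accrual is 10 × (144/169)/3 = 2.84 per month, or one patient every 30.44/2.84 = 10.72 days. Assume even accrual, that the first 15 entered are the 15 analysed, and that all stay on treatment. When the 15th completes cycle 2, patient i has d(i) = 56 + 10.72 × (15 − i) days of follow-up, from 206 days for the first down to 56 for the last.

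- Planned doses: 1 patient with 1, 5 with 2, 5 with 3 and 4 with 4; mean 42/15 = 2.8.
- 14 of 15 have passed the second dose date.
- 9 of 15 have a full 8 weeks after it (d ≥ 112).

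**4. Illustration of sensitivity.** The documents do not say what share of the risk falls early, so everything here is assumed. Take a true cumulative colitis risk of 33%, three times the benchmark. In the even scenarios it accrues at constant hazard over T = 16 or 24 weeks: risk by day d = 1 − 0.67^(min(d, T)/T), with d and T in the same units. In the early scenario three quarters falls in the first 8 weeks; where follow-up continues, the rest accrues linearly to T. With uneven follow-up, P is the upper tail of a sum of 15 independent events with these individual risks.

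| Colitis, P(5 or more of 15) | Even, 16 wk | Even, 24 wk | Three quarters early |
|---|---|---|---|
| Events cut at 8 weeks (risk 18.1%, 12.5%, about 25%) | 12% | 3% | 31% |
| Existing look, all follow-up counted | 48% | 33% | 48-53% |
| Same patients, last at end of cycle 4 period | 59% | 52% | 56-59% |
| Full observation | 59% | 59% | 59% |

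For pneumonitis at an assumed 15%, P(3 or more of 15) with even accrual of risk over 16 or 24 weeks is:

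- 11% or 4% if events are cut at 8 weeks;
- 33% or 24% at the existing look with all follow-up counted;
- 40% or 35% at the later look;
- 40% with full observation.

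**The case against.** The strongest reply is that completing two cycles defines who is analysed, not which events count. That is right. A reader might infer that the check closes on day 56 and that every Arm C patient has then had exactly one ipilimumab dose. The text sets no such cutoff, and at planned accrual 14 of 15 patients would be past the second dose date. One dose is the guaranteed minimum. Slower accrual would lengthen exposure.

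A reader might also infer that 11% and 3% are whole-treatment rates. That is plausible, but section 9.8.2 cites only prior studies and gives no period, so a mismatch cannot be demonstrated, only not ruled out.

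The ipilimumab adverse event list (section 5.3.3, footnote 2) says most immune-mediated reactions appeared early in treatment, with a minority weeks to months after stopping. This favours the early scenario and makes the 3% and 12% figures look pessimistic. It gives no share by week 8, so it does not settle the size.

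Later events are not unmonitored. Section 5.2.10 requires 24-hour reporting of treatment-related grade 3-5 colitis and pneumonitis, section 5.3.3 overrides the colitis reporting exception for Arm C, section 5.2.8.2 covers events beyond 30 days, and twice-yearly toxicity analyses continue. All of this stands and limits the harm. None of it supplies a numeric criterion.

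**Conclusion.** The concern holds as a gap in specification and timing. The only numeric triggers are applied once, at a milestone guaranteeing one ipilimumab dose. Neither the event cutoff nor the benchmark exposure is stated, and no numeric criterion applies afterwards.

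The size of the loss cannot be derived from the documents. The direction can: for a given true risk, a shorter counting window cannot raise the chance of reaching the trigger. At the assumed 33% colitis risk, stating that all follow-up counts recovers much of the loss, and a later look adds more: from 33-48% to 52-59% under even accrual of risk, and from 48-53% to 56-59% if risk is mostly early. These ranges rest on the assumed risk, the onset patterns, even accrual at the planned rate, and every patient remaining at risk over the follow-up counted.

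The change is worth making because it is cheap and serves patient safety. The thresholds themselves are not wrong.

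**What to change.** Keep the two-cycle look and amend section 9.8.2 as follows:

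1. State that every grade 3-5 treatment-related colitis or pneumonitis event up to a named data cutoff is counted, including events after treatment stops.
2. State the treatment and follow-up period behind the 11% and 3%, or say that it is not known.
3. Reapply the same 5/15 and 3/15 counts to the same 15 patients per arm once the last of them has reached the end of the cycle 4 period (4 × 28 = 112 days), whether or not still on treatment. The consequence stays advisory.

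The second application comes 56 days after the first. On the accrual in step 3 that is day 206 + 56 = 262 from first Arm C entry. About 25 of the 48 planned Arm C patients (144/3) would then be enrolled (262/10.72 = 24.4 intervals after the first patient), so the result can still protect later patients.

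The cost is one paragraph and one extra table from data already collected, with no accrual pause. The downside is a slightly higher chance of a false advisory trigger. Counts accumulate in the same patients, so an arm that meets a trigger at the first look also meets it at the second. The overall chance per arm is therefore that of the second look alone: at most about 1.9% for colitis at a true 11% and 0.9% for pneumonitis at a true 3%.
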